7. OUTCOME MEASURES

7.1 Primary Outcome

- **Measure:** Sleep Quality.
- **Instrument:** Pittsburgh Sleep Quality Index (PSQI) - Indonesian validated version.
- **Time Frame:** Baseline (Pre-test) and Post-intervention (Post-test, after [X] weeks).
- **Metric:** Total PSQI score (Range 0-21; lower scores indicate better sleep quality).

7.2 Secondary Outcomes

- **Anxiety Levels:** Measured using the Hamilton Anxiety Rating Scale (HARS).
- **Hemodynamics:** Systolic and Diastolic Blood Pressure.

7.3 Confounding Variables

- Age, Parity, BMI, Gestational Age.

8. STATISTICAL ANALYSIS PLAN

8.1 Data Management

Data is collected via paper questionnaires and entered into a digital database (SPSS). Data cleaning is performed to check for outliers and missing values.

8.2 Statistical Methods

- **Descriptive Statistics:** Means/Standard Deviations for continuous variables; Frequencies/Percentages for categorical variables.
- **Baseline Comparability:** Independent t-tests or Chi-square tests to ensure groups are balanced at baseline (specifically checking HARS and Diastolic BP as noted in preliminary analysis).
- **Outcome Analysis:** A **Linear Mixed Model** is used to analyze the difference between groups while adjusting for baseline scores and confounding variables (e.g., Age, Parity).
- **Significance Level:** p-value < 0.05.

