2.3 Research Hypothesis

1. There is a significant difference in sleep quality scores between pregnant women performing traditional pregnancy exercises and those performing stretching exercises.
2. Both exercise modalities will result in improved sleep quality scores compared to baseline.

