4. STUDY DESIGN

4.1 Study Type

- **Type:** Interventional (Clinical Trial)
- **Design:** Quasi-Experimental (Non-randomized trial)
- **Allocation:** Non-randomized Parallel Assignment (Two Arms)
- **Masking:** Open Label (Participants and instructors know the intervention; Outcome assessors should ideally be blinded if possible).

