5. STUDY POPULATION

5.1 Sample Size

Total sample size: N = 60

- Intervention Group: n = 30
- Control (Comparator) Group: n = 30

$$n = 2 \left[\frac{\left(Z_{1-\frac{\alpha}{2}} + Z_{1-\beta} \right) S}{X_1 - X_2} \right]^2$$
$$n = 2 \left[\frac{(1,96 + 0,84)2,9910925540121}{6,84 - 10,10} \right]^2$$
$$n = 2 \left[\frac{(2,8)2,9910925540121}{-3,26} \right]^2$$

$$n = 2 \left[\frac{8,3750591512338}{-3,26} \right]^2$$

$$n = 2[-2,569036549458]^2$$

$$n = [-5,138073098916]^2$$

$$n = [26,399795169806]$$

$$n = 26,399795169806 \text{ adding } 10\%.$$

Therefore, a minimum of 30 respondents per group is required

S value is calculated in the following:

$$S = \sqrt{\frac{S_1^2(n_1 - 1) + S_2^2(n_2 - 1)}{n_1 + n_2 - 2}}$$

$$S = \sqrt{\frac{2,86^2 (39 - 1) + 3,12^2 (38 - 1)}{39 + 38 - 2}}$$

$$S = \sqrt{\frac{2,86^2 (39 - 1) + 3,12^2 (38 - 1)}{39 + 38 - 2}}$$

$$S = \sqrt{\frac{8,1796(38) + 9,7344(37)}{75}}$$

$$S = \sqrt{\frac{310,8248 + 360,1728}{75}}$$

$$S = \sqrt{\frac{670,9976}{75}}$$

$$S = \sqrt{\frac{670,9976}{75}}$$

$$S = \sqrt{8,9466346666}$$

$$S = 2,9910925540121$$

Notes :

n : Sample size
 Z : Z-score
 $Z_{1-\alpha/2}$: 1.96 at the 95% confidence interval
 $Z_{1-\beta}$: Statistical power at 0.84
 S : Standar deviasi gabungan
 $X_1 - X_2$: The minimum significant mean difference observed in prior research (6,84) ($6,84 - 10,10 = -3,26$) (Blanquea,dkk. 2018)
 S : Weighted average of standard deviations from two groups (2,99)
 S_1 : Standard deviation in group 1 (2,86) (Blanquea,dkk. 2018)
 n_1 : Sampel size in group 1 (39)
 S_2 : Standard deviation in group 2 (3,12) (Blanquea,dkk. 2018)
 n_2 : Sampel size in group 2 (38)

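### Does the one-sentence linear mixed model in section 8.2 have to be rewritten as a post-test ANCOVA?

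*Combined protocol and SAP*

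**What the plan says.** Section 8.2 gives the outcome analysis in one sentence: a linear mixed model "is used to analyze the difference between groups while adjusting for baseline scores and confounding variables (e.g., Age, Parity"), tested at p < 0.05. Section 7.1 sets two PSQI assessments, "Baseline (Pre-test) and Post-intervention (Post-test, after [X] weeks"), and takes the total score as the metric. The week number is blank there, but section 4.2 gives three weeks. Section 7.3 names the confounders in full: "Age, Parity, BMI, Gestational Age". Section 4.1 describes the allocation as "Non-randomized Parallel Assignment (Two Arms").

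Section 2.3 adds a second hypothesis: "Both exercise modalities will result in improved sleep quality scores compared to baseline". Section 8.2 names no separate analysis for it. The effect behind the sample size in section 5.1 is described as "The minimum significant mean difference observed in prior research (6,84"), worked out there as 6.84 - 10.10 = -3.26 points.

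**The concern.** A mixed model is normally fitted to repeated rows per person, and the only repetition here is pre-test and post-test. An analyst who wants to use a mixed model and also adjust for baseline could stack both rows and enter baseline as a covariate. Baseline would then appear on both sides of the equation.

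Two consequences would follow. Without a group-by-time term, the group coefficient averages over a row measured before any exercise, so the reported effect is diluted. With that term, the interaction is the raw difference in change, and the promised adjustment does not touch it. Two analysts working from the same sentence could therefore report different primary effects. The arms may also differ at baseline because allocation is not randomized, and the choice between baseline adjustment and change from baseline would then affect the answer.

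**Working it through.** **Inputs from the documents.** 30 women per arm, difference 3.26 and pooled SD 2.991 (section 5.1); one pre-test and one post-test (7.1); four confounders (7.3).

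**Assumed, not in the documents.** Pre-post correlation r = 0.3 / 0.5 / 0.7, equal pre-test and post-test SDs unless stated, independent confounders, complete pairs. The simulated results rest on 12,000 trials per setting, with Monte Carlo error of at most about 0.7 percentage points.

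**The plan's own figures.** S = sqrt(670.9976 / 75) = 2.991, as printed. The printed formula gives 2 x 2.569^2 = 13.2 per group. The printed 26.4 arises because the factor 2 was squared too: (2 x 2.569)^2 = 26.4. That is a separate slip, and it makes the trial larger than its formula requires. The planned 30 per arm is used below.

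**Reading A: post-test rows only, baseline as covariate.** With one row per woman, a random intercept cannot be separated from the residual. The model reduces to post-test = b0 + b1 x group + b2 x baseline + confounders + error, which is ANCOVA. Results for the three correlations:
- Mean effect: 3.26 / 3.27 / 3.27
- Coverage of the 95% CI: 94.9% / 94.6% / 95.2%
- Type I error: 5.2% / 5.1% / 5.2%

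**Reading B: both rows stacked, baseline also a covariate, group main effect tested.** On complete pairs the group coefficient comes from regressing (pre + post) / 2 on group, baseline and confounders. The pre-test half contributes zero, because baseline given baseline leaves nothing for group to explain. The coefficient is therefore (0 + b1) / 2, and 3.26 / 2 = 1.63.
- Simulated mean: 1.63 / 1.64 / 1.63
- Interval contains 3.26: 4.6% / 1.7% / 0.2% of trials
- Power: 96.9% / 99.0% / 100%
- Type I error: 2.7% / 3.4% / 4.1%

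Actual REML fits show the same ratio, for example -1.891 against an ANCOVA effect of -3.781.

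**Reading C: as B, with group-by-time tested.** The interaction is a within-woman contrast, so covariates that are constant within a woman cancel. In one dataset it was -3.44888 with and without baseline and confounders, equal to the raw change difference.
- Type I error, random-intercept variance held at zero or above: 7.5% / 7.0% / 6.1%
- Type I error, compound-symmetry covariance allowed to be negative: 5.2% / 5.3% / 5.0%

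**Non-randomized allocation.** With the same covariates in both analyses, ANCOVA and change-score estimates differ in size by (1 - b2) x baseline imbalance, where b2 = r x SD(post) / SD(pre). For an assumed 1-point imbalance and equal SDs the gap is 0.7 / 0.5 / 0.3 points. At r = 0.5 with an SD ratio of 0.8 or 1.2, b2 is 0.4 or 0.6 and the gap is 0.6 or 0.4. Rejection of a true null:
- Post-test depends on baseline as ANCOVA assumes: change score 11.4% / 9.9% / 8.0%, ANCOVA 4.9% / 5.1% / 5.0%
- Arms differ by a stable amount: ANCOVA 14.8% / 10.7% / 7.8%, change score 5.2% / 5.2% / 5.2%

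**Size of the trial.** Using n = 2 x (2.8 x SD / 3.26)^2, the ANCOVA SD is S x sqrt(1 - r^2) = 2.853 / 2.590 / 2.136, so 13 / 10 / 7 per arm. The change-score SD is S x sqrt(2(1 - r)) = 3.539 / 2.991 / 2.317, so 19 / 14 / 8. Thirty per arm covers every case, before or after the 10% allowance.

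**The case for a change.** The strongest case for a change is that the sentence does not identify the model, that stacking is what the words mixed model suggest, and that in a non-randomized trial an open choice between baseline adjustment and change score invites a decision made after seeing the data. Writing ANCOVA out would cost a few sentences, and section 8.1 already has the data going into SPSS ("Data is collected via paper questionnaires and entered into a digital database (SPSS")).

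Part of this stands. The sentence is thin, the algebra of readings B and C is right on complete pairs, and the name mixed model fits poorly with one post-test. But reading B needs two steps that the plan does not take: making baseline an outcome row as well as a covariate, and then testing an effect averaged over an untreated row. Reading C tests a contrast that baseline adjustment cannot reach, which conflicts with the sentence's stated purpose. The choice between baseline adjustment and change score is not fully open either, because section 8.2 already says that baseline is adjusted for. The short confounder list there is introduced as an example, and section 7.3 completes it.

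Rewriting is also not a clear gain. Under non-randomized allocation the preference for ANCOVA over change score is a trade-off, as the rejection rates show. A more detailed mixed model can go wrong too. With both times as outcomes and no baseline covariate, the group-by-time contrast in one dataset stayed at -3.6236 with or without confounder main effects, against -3.132 from adjusted ANCOVA. It would need confounder-by-time terms to deliver the adjustment that the plan promises.

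The missing analysis for the second hypothesis is a separate and minor matter. Within-group change follows directly from the two scores collected.

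**Conclusion.** No change follows. Section 8.2 leaves out detail, but it does not prescribe a faulty analysis. Its plain reading is post-test PSQI adjusted for baseline and the four listed confounders, which is ANCOVA and performs as it should at the plan's inputs (type I error 5.1% to 5.2%, coverage 94.6% to 95.2%). The halved effect and the unadjusted interaction belong to fits that the plan does not state. Even reading B would leave the test conservative, with power of at least 96.9%; the damage would be to the reported size and interval. The inflation in reading C reaches 7.5% at most, and only when the random-intercept variance is held at zero or above.

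The remaining choice, ANCOVA or change score when arms are not randomized, is a fair trade-off. The two differ by 0.3 to 0.7 points per point of baseline imbalance, and neither is safe under both assumptions.

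These figures rest on assumed correlations of 0.3 to 0.7, equal pre-test and post-test SDs, independent confounders and complete pairs. With missing post-tests, the factor of one half in reading B is only approximate.

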6.2 Group B: Stretching Exercise (Active Control Group)

- **Description:** A regimen focusing on static stretching and flexibility.
- **Components:** Gentle stretching of major muscle groups (calves, hamstrings, lower back, neck) to relieve tension and improve circulation without the aerobic or intensive strengthening components of the traditional class.
- **Frequency:** Matched to Group A.
- **Duration:** Matched to Group A.

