6.3 Adherence Monitoring

Participants will utilize a logbook to record exercise sessions. Attendance at supervised sessions will be recorded by the instructor.

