2	Gluteus Maksimal		
Lying on the surface, with one lower limb in flexion and external rotation of the hip and knee, and the ankle resting on the contralateral thigh, the therapist manually increases hip flexion towards the opposite shoulder (3 x 20-second repetitions, bilateral and alternating).

3	Piriformis		
Lying on the surface with one lower limb in flexion and external rotation of the hip and knee, and the ankle resting on the contralateral thigh, the therapist manually conducts hip adduction towards the opposite lower limb (3 x 20-second repetitions, bilaterally and alternating).

4	Paravertebral		
Sitting on the edge of a surface with abducted lower limbs and feet resting on the floor. Perform trunk flexion for freight and sideways while supported up on a Swiss grid ball (3 x 15 sec reps, bilaterally and alternating).

5	Kuadratus Lumborum		
The therapist manually stretches the lumbar square in lateral decubitus, performing two 20-second repetitions on each side.

6	Latissimus Dorsi		
In a supine position with the upper extremities in 180° flexion, the therapist manually lateralises the pregnant woman's upper trunk to contralateral elongation (2 x 20 second repetitions, bilaterally).

7	Skalane		
The therapist conducts cervical rotation and flexion in a supine position to lengthen the contralateral scalene (2 x 20 second repetitions, bilaterally).

8	Trapezius		
The therapist conducts lateral tilt and cervical flexion to the contralateral trapezius in a supine position, with two 20-second repetitions performed bilaterally.

Source: (Fontana Carvalho et al., 2020)

Fontana Carvalho, A. P., Dufresne, S. S., Rogerio de Oliveira, M., Couto Furlanetto, K., Dubois, M., Dallaire, M., Ngomo, S., & da Silva, R. A. (2020). Effects of lumbar stabilization and muscular stretching on pain, disabilities, postural control and muscle activation in pregnant woman with low back pain. *Eur J Phys Rehabil Med*, 56(3), 297-306.
<https://doi.org/https://doi.org/10.23736/S1973-9087.20.06086-4>

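### The planned mixed model makes no provision for women who share a class, instructor or therapist; if their PSQI scores correlate, the standard error is too small and type I error exceeds 5%.

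*Combined protocol and SAP*

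**What the plan says.** **Delivery.** Section 6.3 states: "Attendance at supervised sessions will be recorded by the instructor". Section 6.2 describes stretching as "without the aerobic or intensive strengthening components of the traditional class"; this is the only place where Group A's programme is called a class. Section 6.1 describes Group A without mentioning a class and leaves frequency and supervision as an unfilled placeholder. Figure S2 gives the stretching movements. One reads "The therapist manually stretches the lumbar square in lateral decubitus", and a therapist acts in seven of the eight. The plan does not give the number or size of classes, or the number of instructors or therapists.

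**Analysis.** Under section 8.2, a linear mixed model "is used to analyze the difference between groups while adjusting for baseline scores and confounding variables (e.g., Age, Parity"). No random effect or covariance structure is named. Section 7.3 lists the confounders as age, parity, BMI and gestational age, all properties of the individual woman. Section 8.2 tests at 0.05.

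**Sample size.** Section 5.1 uses the two-sample formula for independent observations, with no ICC, cluster size or design effect, and concludes: "Therefore, a minimum of 30 respondents per group is required".

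**The concern.** Women taught together, or handled by the same therapist, share the provider's skill, enthusiasm and pace, and in a class they share one another's company. Sleep scores within such a group may therefore be more alike than scores across groups. A model that leaves the level out counts 30 women per arm as 30 independent pieces of information when there are fewer. The confidence interval for the primary comparison is then too narrow, and differences between classes or providers can pass for a difference between exercise types.

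In the limiting case of one instructor or therapist per arm, provider and exercise type coincide, and no model can tell them apart. The plan does not acknowledge this possibility.

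Timing matters too. Section 6.3 plans a record of attendance but not of which class or provider each woman had, so the missing level may be impossible to fit later.

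**Working it through.** **1. The plan's own figures.** From section 5.1: SDs 2.86 (n = 39) and 3.12 (n = 38), difference 10.10 − 6.84 = 3.26, Z values 1.96 and 0.84 (the latter labelled "Statistical power at 0.84", although it is the normal quantile for 80% power).

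- Pooled SD = √(670.9976/75) = 2.991, as printed.
- (2.8 × 2.991)/3.26 = 2.569, as printed.
- n = 2 × 2.569² = 13.2 per group. The plan prints 26.4 because it moves the 2 inside the square: (2 × 2.569)² = 26.4. Adding 10% gives 29.04, hence 30.

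The algebra slip is a separate matter. It bears on this point only because it leaves 30 per group with spare power.

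**2. Formulas for clustering.** The cluster size m and the ICC are assumptions, because the documents give neither.

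- Design effect: DE = 1 + (m − 1) × ICC.
- Both arms clustered: the true SE is √DE times the naive SE.
- Only Group A clustered, equal arms: the factor is √f, with f = (DE + 1)/2.
- True two-sided level of a nominal 5% test: 2 × [1 − Φ(1.96/√DE)], or the same with f in place of DE.

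Worked case, m = 10 and ICC 0.05: DE = 1 + 9 × 0.05 = 1.45; √1.45 = 1.204; 1.96/1.204 = 1.628; level = 10.4%. For Group A only: f = (1.45 + 1)/2 = 1.225; √1.225 = 1.107; level = 7.7%.

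| Women per cluster | ICC | DE | Level, both arms | Level, Group A only |
|---|---|---|---|---|
| 5 | 0.02 | 1.08 | 5.9% | 5.5% |
| 5 | 0.05 | 1.20 | 7.4% | 6.2% |
| 5 | 0.10 | 1.40 | 9.8% | 7.4% |
| 10 | 0.02 | 1.18 | 7.1% | 6.0% |
| 10 | 0.05 | 1.45 | 10.4% | 7.7% |
| 10 | 0.10 | 1.90 | 15.5% | 10.4% |
| 30 (one per arm) | 0.05 | 2.45 | 21% | 13.6% |

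A simulation of 8,000 runs, both arms clustered, gave 7.7%, 7.1%, 10.3%, 16.3% and 21.4% for (5, 0.05), (10, 0.02), (10, 0.05), (10, 0.10) and (30, 0.05), in line with the formula. A t-test on class means held 5.0% to 5.3%.

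**3. Price of the correct analysis.** Power for 3.26 points, SD 2.991, 30 per arm, both arms clustered, ICC 0.05, noncentral t with (number of clusters − 2) degrees of freedom:

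| Clusters per arm | SE = 2.991 × √(2 × DE/30) | df | Power |
|---|---|---|---|
| 6 of 5 | 0.846 | 10 | 93% |
| 3 of 10 | 0.930 | 4 | 75% |
| 2 of 15 (DE 1.70) | 1.007 | 2 | 43% |
| None (independence) | 0.772 | 58 | 98.6% |

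With one cluster per arm no degrees of freedom remain, and the comparison cannot be tested at that level.

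**The case against.** Several objections have force.

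- **The model is unspecified, not shown to be wrong.** A reader might infer that the plan treats all 60 women as independent. Section 8.2 does not say so: it names a mixed model and no random effect, so a class or provider term is neither included nor excluded. This stands, and the point is therefore one of missing provision.
- **Class delivery is thinly documented.** For Group A it rests on one phrase in the description of the other arm. Group B reads as one-to-one handling, where only therapist-level clustering could arise. This also stands, and is why the Group A only figures are shown.
- **The harm is conditional.** A reader might infer that the standard error and p-value are certainly too small. That requires a positive ICC and several women per class or provider, and the documents establish neither.
- **Thirty per group is not shown to be too few.** The correct formula gives 13.2, so 30 absorbs a design effect of up to 30/13.2 = 2.27 at 80% power by the normal approximation. This stands as far as it goes. The slack protects power; it does not protect type I error or the width of the interval. Few clusters would still cost power through degrees of freedom, but their number is unknown.
- **Other threats come first.** Allocation is non-randomized, so the 5% level is already exposed to selection and confounding, and the section 6.1 placeholders must be filled before clusters can be described. Both are true, but neither removes this problem, and covariate adjustment does not address it.

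**Conclusion.** The point holds in conditional form. The documents describe provider-led delivery, while the planned analysis lists only baseline and woman-level covariates and names no random effects. If women share a class, instructor or therapist and their PSQI scores correlate, following section 8.2 as written gives too small a standard error.

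Over the assumed range, the excess over 5% runs from under one percentage point to about ten with both arms clustered, and from about half a point to about five with only Group A clustered. One cluster of 30 per arm at ICC 0.05 is the severe case. These sizes assume equal clusters and the normal approximation; none is an estimate from trial data.

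The documents do not support a claim that the sample size is inadequate, or that instructors must be shared between arms, which would alter delivery and staffing. The change should be made because it is cheap and because the identifiers may not be recoverable later.

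**What to change.** 1. **Section 6.3:** record a class ID and an instructor or therapist ID for each woman on the existing attendance record. If sessions have already been held, recover these from the instructors' records where possible.
2. **Section 8.2:** state the random effects. Where an arm has more than one class or provider, add a random intercept for that level (Group A by class; Group B by therapist if delivered one-to-one), with Kenward-Roger or Satterthwaite degrees of freedom.
3. **If an arm has only one class or provider:** state that the result cannot separate exercise type from provider. A random intercept cannot repair this.

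**Cost:** one or two columns on a form already in use and a few sentences of SAP text. The statistical price is a wider interval and, with few clusters, the lower power shown in the second table. No change to the sample size or to instructor rostering is needed.

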9. ETHICS AND SAFETY

9.1 Ethical Approval

This protocol will be submitted to the Ethical Review Board of [Insert Name, e.g., Health Polytechnic of Palangka Raya].

[figure not shown]
[figure not shown]
9.2 Informed Consent

[figure not shown]
[figure not shown]
Written informed consent will be obtained from all participants prior to enrollment. Participants will be informed of the benefits and potential risks of physical activity during pregnancy.

[figure not shown]
9.3 Safety Monitoring

Participants will be monitored for any adverse events (dizziness, contractions, pain). The intervention will be stopped immediately if any warning signs of pregnancy complications occur.

Figure S1. Traditional Pregnancy Exercise

No	Movement	Position	
1	Warm-up		
Position: Standing, feet shoulder-width apart.
 
Instructions:
 
 • Begin with slow breathing: inhale through the nose, exhale through the mouth. • Gently roll shoulders forward and backward 5–10 times. • Rotate the neck slowly in both directions. • March lightly in place for 1–2 minutes to warm the muscles. 
Purpose: Prepare the body, increase circulation, and reduce injury risk.

2	Deep Breathing and Chest Opening		
Position: Standing or sitting upright
 
Instructions:
 
 • Place both hands on the sides of the ribcage. • Inhale deeply, expanding the chest and ribs outward. • Exhale slowly while relaxing the shoulders. • Repeat 8–10 times. 
Purpose: Improve oxygenation, reduce tension, and promote relaxation.

[figure not shown]
[figure not shown]
3	Pelvic Tilts		
Position: Standing with back against a wall or on hands and knees
 
Instructions:
 
 • Gently tilt the pelvis forward and backward, tightening the abdominal muscles. • Avoid arching the lower back excessively. • Perform 10–12 repetitions. 
Purpose: Reduce lower-back discomfort and strengthen core stability.

4	Cat–Cow Stretch		
Position: Hands and knees (“tabletop” position)
 
Instructions:
 
 • Inhale while dropping the belly and lifting the head (cow). • Exhale while rounding the back and tucking the chin (cat). • Move slowly with the breath for 10 cycles. 
Purpose: Relieve back tension and improve spinal flexibility.

5	Hip Circles		
Position: Standing, hands on hips
 
Instructions:
 
 • Gently rotate the hips in a circular motion clockwise for 10 repetitions. • Repeat counterclockwise for another 10 repetitions.

[figure not shown]
[figure not shown]
			
Purpose: Loosen pelvic muscles and prepare for childbirth.

6	Side Stretch		
Position: Standing or sitting
 
Instructions:
 
 • Raise the right arm overhead and gently bend to the left. • Hold for 10–15 seconds while breathing normally. • Switch sides and repeat. 
Purpose: Stretch the torso, reduce ribcage tightness, and improve breathing comfort.

7	Squat with Support		
Position: Standing, holding a chair or wall for balance
 
Instructions:
 
 • Slowly lower into a comfortable squat, keeping feet wide and knees aligned. • Hold for 5–10 seconds, then rise slowly. • Repeat 8–10 times. 
Purpose: Strengthen legs and pelvic floor, improve hip flexibility.

8	Butterfly Stretch		
Position: Sitting on the floor
 
Instructions:
 
 • Bring the soles of the feet together and let the knees fall outward. • Hold the ankles and gently press

[figure not shown]
[figure not shown]
			
the knees toward the floor.
 
 • Maintain the stretch for 20–30 seconds. 
Purpose: Open the hips and improve pelvic flexibility.

9	Pelvic Floor (Kegel) Exercise		
Position: Sitting or lying down
 
Instructions:
 
 • Contract the pelvic floor muscles as if stopping urine flow. • Hold for 5 seconds, then relax for 5 seconds. • Repeat 10–15 times. 
Purpose: Strengthen pelvic muscles to support pregnancy and childbirth.

10	Ankle and Leg Stretch		
Position: Sitting with legs extended
 
Instructions:
 
 • Point and flex the feet 10 times. • Rotate ankles clockwise and counterclockwise 10 times each. • Gently stretch the calves by pulling toes toward the body. 
Purpose: Improve circulation and reduce leg cramps or swelling.

11	Cool-Down and Relaxation		
Position: Sitting or lying on the left side
 
Instructions:
 
 • Take slow, deep breaths for 1–2 minutes.

[figure not shown]
			
• Relax the shoulders, jaw, and hands.• Visualize calmness and release tension throughout the body. 
Purpose: Lower heart rate, promote relaxation, and complete the session safely.

--	--	--	--

Figure S2. Stretching Exercise

No	Movement	Position	
1	Iskium Tibialis		
Lying on the surface, the therapist elevates the lower limb in extension and ankle dorsiflexion (3 x 20 sec repeats, bilaterally and alternately).

2	Gluteus Maksimal		
Lying on the surface, with one lower limb in flexion and external rotation of the hip and knee, and the ankle resting on the contralateral thigh, the therapist manually increases hip flexion towards the opposite shoulder (3 x 20-second repetitions, bilateral and alternating).

3	Piriformis		
Lying on the surface with one lower limb in flexion and external rotation of the hip and knee, and the ankle resting on the contralateral thigh, the therapist manually conducts hip adduction towards the opposite lower limb (3 x 20-second repetitions, bilaterally and alternating).

4	Paravertebral		
Sitting on the edge of a surface with abducted lower limbs and feet resting on the floor. Perform trunk flexion for freight and sideways while supported up on a Swiss grid ball (3 x 15 sec reps, bilaterally and alternating).

5	Kuadratus Lumborum		
The therapist manually stretches the lumbar square in lateral decubitus, performing two 20-second repetitions on each side.

6	Latissimus Dorsi		
In a supine position with the upper extremities in 180° flexion, the therapist manually lateralises the pregnant woman's upper trunk to contralateral elongation (2 x 20 second repetitions, bilaterally).

7	Skalane		
The therapist conducts cervical rotation and flexion in a supine position to lengthen the contralateral scalene (2 x 20 second repetitions, bilaterally).

8	Trapezius		
The therapist conducts lateral tilt and cervical flexion to the contralateral trapezius in a supine position, with two 20-second repetitions performed bilaterally.

Source: (Fontana Carvalho et al., 2020)

Fontana Carvalho, A. P., Dufresne, S. S., Rogerio de Oliveira, M., Couto Furlanetto, K., Dubois, M., Dallaire, M., Ngomo, S., & da Silva, R. A. (2020). Effects of lumbar stabilization and muscular stretching on pain, disabilities, postural control and muscle activation in pregnant woman with low back pain. *Eur J Phys Rehabil Med*, 56(3), 297-306.
<https://doi.org/https://doi.org/10.23736/S1973-9087.20.06086-4>
